17.1.7. ADDITIONAL AE SUMMARIES

17.1.7.1. AEs by exposure interval at earliest onset

AEs will be summarized by SOC and PT by exposure intervals. If there are multiple occurrences of one TEAE, only the first incidence will be summarized. Denominators for exposure intervals will be based on the number of subjects who were exposed as of the first day of the interval. For cases where the events meet the treatment-emergent definition but start after the last dose of study medication, the exposure interval for the event will be considered the interval of the last day of exposure to study medication.

Exposure categories to be assessed are the following:

- For all subjects up to Week 28: 1-56 days, 57-112, 113-168 and \geq 169 days.
- For all Japanese subjects up to Week 52: 1-56 days, 57-112, 113-168, 169-224, 225-280, 281-336 and \geq 337 days.

An additional summary will be presented for Treatment-Emergent Adverse Events Occurring in at Least 3% of Subjects broken down by exposure categories for all subjects up to Week 28 overall.

17.1.7.2. TEAEs \geq 3%

A summary of TEAEs with an incidence of \geq 3% of subjects will be presented by Preferred Term and treatment group. Summaries will be provided for the safety population. This summary will be repeated separately for all Japanese subjects up to Week 52 of TEAEs with an incidence of \geq 3% of subjects, and repeated by Most Recent or Current Episode subgroup separately as well.

17.1.7.3. Combined PTs

A summary of TEAEs by combined PT will be presented by SOC and PT, where combined PT will be determined by medical review of coded AE terms prior to database lock. The list of combined PT can be found in Appendix 3. This summary will be repeated for all Japanese subjects up to Week 52 separately as well.

17.1.7.4. AEs by PT by descending frequency

A summary of AEs by PT by descending frequency will be presented by treatment group. This summary will be repeated for all Japanese subjects up to Week 52 separately as well.

17.2. DEATHS

If any subjects died during the study, the information will be presented in a data listing. Deaths will be recorded on either the AE panel as an AE leading to death ("Fatal" AE), or on the C-SSRS panel as a lethal suicide attempt.

Document:	K:\DSP\SM-13496\RVA97109\Biostatistics\Documentation\SAP		
Author:	[REDACTED]	Version Number:	1.0
		Version Date:	20MAR2018

Template No: CS_TP_BS016 – Revision 3
Effective Date: 01May2012

Reference: CS_WI_BS005

Copyright © 2012 [REDACTED] All rights reserved.

The contents of this document are confidential and proprietary to [REDACTED]. Unauthorized use, disclosure or reproduction is strictly prohibited.

17.3. LABORATORY EVALUATIONS

Results from the central laboratory will be included in the reporting of this study for Hematology, Blood Chemistry and Urinalysis. Endocrine parameters will be summarized separately. A list of laboratory assessments to be presented in the outputs is included in Table 8 of the protocol. Laboratory data will be summarized for the safety population by treatment group.

Presentations will use reported units, except for Chloride, Potassium and Sodium that will use SI Units (International System of Units).

Quantitative laboratory measurements reported as "< X", i.e. below the lower limit of quantification (BLQ), or "> X", i.e. above the upper limit of quantification (ULQ), will be converted to X for the purpose of quantitative summaries, but will be presented as recorded, i.e. as "< X" or "> X" in the listings.

The following summaries will be provided for laboratory data:

- Observed and change from DB baseline and LT baseline to each post-baseline visit including Week 28 (LOCF) endpoint and Week 52 (LOCF) endpoint for subjects within Japan (for quantitative measurements)
- Shift from DB baseline and LT baseline to Week 28 (LOCF) and Week 52 (LOCF) endpoints according to normal range criteria (for quantitative measurements and categorical measurements)
- Summary of subjects meeting markedly abnormal criteria
- Listing of subjects meeting markedly abnormal criteria

The following parameters are presented split by fasting status and overall: HDL cholesterol, LDL cholesterol, total cholesterol, insulin, triglycerides, glucose and homeostasis model assessment of insulin resistance (HOMA-IR). For laboratory variables split by fasting, change from DB baseline and LT baseline will only be calculated where the post-baseline fasting status matches the DB baseline or LT baseline fasting status respectively. Fasting parameters will only be summarized at DB Baseline, LT Baseline, Week 28 and Week 28 (LOCF) visits and at Week 52 and Week 52 (LOCF) for subjects within Japan.

Prolactin will be presented overall and by sex.

17.3.1. LABORATORY SPECIFIC DERIVATIONS

A homeostasis model assessment of insulin resistance (HOMA-IR) (Matthews, Hosker, Rudenski, Naylor, Treacher, & Turner, 1985) parameter must also be calculated and included in summaries. The calculation of the parameter is as follows:

$$\text{HOMA-IR} = \text{Glucose (mg/dL)} \times \text{Insulin (mU/L)} / 405$$

17.3.2. LABORATORY REFERENCE RANGES AND MARKEDLY ABNORMAL CRITERIA

Quantitative laboratory measurements will be compared with the relevant laboratory reference ranges in SI units and categorized as:

- Low: Below the lower limit of the laboratory reference range.
- Normal: Within the laboratory reference range (upper and lower limit included).

Document:	K:\DSP\SM-13496\RVA97109\Biostatistics\Documentation\SAP	Version Number:	1.0
Author:	[REDACTED]	Version Date:	20MAR2018

Template No: CS_TP_BS016 – Revision 3
Effective Date: 01May2012

Reference: CS_WI_BS005

Copyright © 2012 [REDACTED] All rights reserved.
The contents of this document are confidential and proprietary to [REDACTED].
reproduction is strictly prohibited.

Unauthorized use, disclosure or

- High: Above the upper limit of the laboratory reference range.

In addition to the high and low quantitative laboratory assignments (as identified by means of the laboratory reference ranges), markedly abnormal quantitative safety (and other) laboratory assessments will also be identified. Markedly Abnormal Post-Baseline Laboratory Values (MAPLV) for selected laboratory parameters can be found in Table C. The criterion of MAPLV is satisfied if a value falls into the markedly abnormal range. Subjects will be represented in the count of a particular MAPLV if they have experienced that MAPLV at least once during the post-baseline treatment phase, regardless of baseline value, up to and including LOCF endpoints. The number and percentage of subjects with MAPLV will be presented by treatment group for all subjects up to Week 28 overall and repeated for all Japanese subjects up to Week 52 overall separately as well.

Table C: Criteria for Markedly Abnormal Post-Baseline Laboratory Values

Hematology Parameter	Markedly/Abnormal Range
Hemoglobin	Male: ≤ 11.5 g/dL
	Female: ≤ 9.5 g/dL
Hematocrit	Male: $\leq 37\%$
	Female: $\leq 32\%$
WBC	$\leq 2.8 \times 10^9/L$
	$\geq 16 \times 10^9/L$
Neutrophils (percent)	$\leq 15\%$
Eosinophils (percent)	$\geq 10\%$
Platelet Count	$\leq 75 \times 10^9/L$
	$\geq 700 \times 10^9/L$
Clinical Chemistry Parameter	Markedly/Abnormal Range
Alkaline Phosphatase	$\geq 3 \times \text{ULN}$
ALT	$\geq 3 \times \text{ULN}$
AST	$\geq 3 \times \text{ULN}$
Bilirubin	≥ 2.0 mg/dL
Albumin	$< 50\%$ LLN
Glucose (fasting)	< 45 mg/dL
	> 160 mg/dL
Sodium	< 130 mmol/L
	> 150 mmol/L
Potassium	< 3 mmol/L
	> 5.5 mmol/L
Chloride	< 90 mmol/L
	> 115 mmol/L
Blood Urea Nitrogen	≥ 30 mg/dL
Creatinine	≥ 2.0 mg/dL
Creatinine Phosphokinase	$\geq 3 \times \text{ULN}$
HbA1c	$\geq 7.5\%$
Prolactin	$\geq 5 \times \text{ULN}$
Lactate Dehydrogenase	$\geq 3 \times \text{ULN}$
Total Cholesterol (fasting)	≥ 300 mg/dL
LDL Cholesterol (fasting)	≥ 200 mg/dL
Triglycerides (fasting)	≥ 300 mg/dL

Document: K:\DSP\SM-13496\RVA97109\Biostatistics\Documentation\SAP

Author: [REDACTED]

Version Number:

1.0

Version Date:

20MAR2018

Template No: CS_TP_BS016 – Revision 3

Reference: CS_WI_BS005

Effective Date: 01May2012

Copyright © 2012 [REDACTED] All rights reserved.

The contents of this document are confidential and proprietary to [REDACTED] reproduction is strictly prohibited.

Unauthorized use, disclosure or [REDACTED]

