3.5 Sample size

The target number of the enrolled patients in the study is as follows:

- Patients who completed the prior study: 325 patients
- Patients who did not participate in the prior study: 80 patients (Japan only)

Rationale

The percentage of patients who completed the PREVAIL 2 study, which has a study design similar to that of the present study, was 74%. Approximately 65% of patients are estimated to enter the present study based on the number of patients who enrolled into the PREVAIL extension study (D1050256) from the PREVAIL 2 study. On the basis of this information, the sample size for the present study was calculated. From considerations of study duration and enrollment speed, approximately 80 Japanese patients will be expected to enroll in the present study.

4. Patient population

The target disease is bipolar I disorder.

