4.2.2 Patients who did not participate in the prior study

Patients who meet any of the following criteria below will be excluded from the study. If the patient eligibility is uncertain, the investigator should discuss about enrollment of the patient with a medical monitor prior to administration of the study drug.

- 1) Patients who were diagnosed as having an Axis I or Axis II disorder (DSM-IV-TR criteria) other than bipolar I disorder that is primary focus of treatment within 3 months prior to screening.
- 2) Patients have a score ≥ 4 on the MADRS item 10 (suicidal thoughts) at screening or baseline.
- 3) Patients with a “Yes” response to the C-SSRS item 4 (active suicidal ideation with some intent to act, without a specific plan) or item 5 (active suicidal ideation with specific plan and intent) at screening (within 6 months prior to screening) or baseline.
- 4) Patients with imminent risk of suicide or injury to self, others, or property.
- 5) Patients hospitalized involuntarily
- 6) Patients with a history of non-response to an adequate trial of 3 or more of the following: antidepressants, antipsychotics, lithium or VPA during the current episode.
- 7) Patients who received monoamine oxidase (MAO) inhibitor within 21 days prior to screening.
- 8) Patients who received fluoxetine or a combination of olanzapine and fluoxetine within 28 days prior to screening.
- 9) Patients who received any depot antipsychotics (sustained-release formulation) within 90 days prior to screening.
- 10) Patients who received clozapine within 120 days prior to screening.
- 11) Patients who received electroconvulsive therapy within 90 days prior to screening.
- 12) Patients with a history of HIV seropositivity.
- 13) Patients with a history of alcohol/drug abuse (DSM-IV-TR criteria) within 3 months prior to screening or of alcohol/drug dependence (DSM-IV-TR criteria) within 12 months prior to screening. Exceptions include caffeine or nicotine abuse/dependence.
- 14) Patients with a history of hypersensitivity (eg, drug-induced anaphylaxis, rash, urticaria, or other allergic reactions) to more than one distinct chemical class of

drugs.

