- 15) Patients with previous or existing clinically significant complications, such as serious nervous system, endocrine system (including type I diabetes mellitus), hepatic, renal, hematological, respiratory, cardiovascular (including unstable angina, congestive heart failure), gastrointestinal, urological, or other diseases. Patients who have a history of any such diseases and who are considered ineligible for the study by the investigator.
- 16) Patients with acute hepatitis, severe chronic hepatitis or marked hepatic dysfunction.
- 17) Patients with a gastrointestinal disease or a surgical history that may affect drug absorption, distribution, metabolism or excretion.
- 18) Patients with any chronic organic disease of the central nervous system (ie, tumor, inflammation, convulsive seizure, vascular disorder, Parkinson's disease, Alzheimer's disease or other types of dementia, myasthenia gravis, or other degenerative diseases).
- 19) Patients with any mental retardation or persistent neurological findings due to serious head injury.
- 20) Patients with a body mass index (BMI) of $\leq 18 \text{ kg/m}^2$ or $\geq 40 \text{ kg/m}^2$ at screening.
- 21) Patients with previous or existing macular or retinal pigment changes.
- 22) Patients with a previous (within 5 years prior to screening) or existing malignant tumor (excluding appropriately treated basal cell carcinoma of the skin, squamous cell carcinoma, and uterine cervix cancer).
- 23) Patients with a history of neuroleptic malignant syndrome.
- 24) Patients with severe tardive dyskinesia, severe dystonia, or other severe motor dysfunction.
- 25) Patients with an HbA1c (NGSP) value of 8.4% or higher at screening.
- 26) Patients with a history or presence of clinically significant ECG abnormality.
- 27) Patients who have received the study medication (including placebo) in a previous clinical study of SM-13496.
- 28) Patients who are breastfeeding.
- 29) Patients who are currently participating or participated in a clinical study with an investigational or marketed compound or device within 3 months prior to screening or who participated in 3 or more clinical studies within 12 months prior to screening.
- 30) Patients who are otherwise considered ineligible for the study by the investigator.

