9.6.5 Laboratory tests, vital signs, body weight, and 12-lead ECG

Summary statistics for observed values and changes from DB and LT baseline in laboratory tests, vital signs, body weights, and 12-lead ECG parameters will be provided for each visit, Week 28 (LOCF) and Week 52 (LOCF) for all patients and by treatment group in the prior study. Categorical variables will be summarized by presenting shift-tables. Note that summaries at visits after 28 weeks as well as at Week 52 (LOCF) will only be provided for patients enrolled in Japan.

The incidence of markedly abnormal post-baseline laboratory values (MAPLV), markedly abnormal post-baseline vital signs (MAPVS), and prolonged QTc will be summarized for the all patients and by treatment group in the prior study. In these analyses, post-baseline data obtained at unscheduled visits will be taken into consideration. These summaries will be provided for overall (up to 28 weeks and up to 52 weeks, respectively).

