17.5.2. VITAL SIGNS MARKEDLY ABNORMAL CRITERIA

Markedly abnormal quantitative Vital Signs measurements will be identified in accordance with the following predefined markedly abnormal criteria indicated in Table E.

Document:	K:\DSP\SM-13496\RVA97109\Biostatistics\Documentation\SAP	Version Number:	1.0
Author:	[REDACTED]	Version Date:	20MAR2018

Template No: CS_TP_BS016 – Revision 3
Effective Date: 01May2012

Reference: CS_WI_BS005

Copyright © 2012 [REDACTED] All rights reserved. [REDACTED] Unauthorized use, disclosure or reproduction is strictly prohibited.

Table E: Criteria for Markedly Abnormal Vital Signs

Variable	Unit	Low	High
Pulse rate	Bpm	≤ 50 bpm AND change from baseline ≤ -15 bpm	≥ 120 bpm AND change from baseline ≥ 15 bpm
SBP	mmHg	≤ 90 mmHg AND change from baseline ≤ -20 mmHg	≥ 180 mmHg AND change from baseline ≥ 20 mmHg
DBP	mmHg	≤ 50 mmHg AND change from baseline ≤ -15 mmHg	≥ 105 mmHg AND change from baseline ≥ 15 mmHg
Body temperature	°C	NA	≥ 38.3 °C AND change from baseline ≥ 0.8 °C
Weight	Kg	percentage change from baseline ≤ -7.0 %	percentage change from baseline ≥ 7.0 %

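### The markedly abnormal laboratory count ignores baseline, so patients who start in the marked range (possible for HbA1c under the new-recruit entry limit) are counted in an incidence

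*SAP*

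**What the plan says.** SAP 17.3.2 uses an absolute criterion: "The criterion of MAPLV is satisfied if a value falls into the markedly abnormal range". A subject enters the count for a parameter "if they have experienced that MAPLV at least once during the post-baseline treatment phase, regardless of baseline value". Table C sets the HbA1c limit at 7.5% or above. Counts and percentages are shown by treatment group, for all subjects up to Week 28 and for Japanese subjects up to Week 52.

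Protocol 9.6.5 plans the same output under the word incidence: "The incidence of markedly abnormal post-baseline laboratory values (MAPLV)". Unscheduled post-baseline values also count.

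On entry, Protocol 4.2.2 (criterion 25) excludes "Patients with an HbA1c (NGSP) value of 8.4% or higher at screening". That section covers only patients who were not in the prior study, with a target of 80, all in Japan. Protocol 4.2.1, for the 325 planned completers of the prior study, sets no HbA1c limit.

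The vital-sign criteria in SAP Table E all include a change from baseline. For a high pulse rate the criterion is "≥ 120 bpm AND change from baseline ≥ 15 bpm".

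**The concern.** A reader takes an incidence to mean new occurrences. Under the SAP rule, the MAPLV percentage mixes patients who moved into the marked range on study with patients who were there on Day 1. For HbA1c the plan's own limits allow the second kind: values from 7.5% to just below 8.4% at screening are eligible and already marked. For triglycerides, cholesterol, creatine phosphokinase and prolactin, the listed entry criteria set no numeric limit, so the same mixing is possible.

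There is no concurrent control group to show how much of the count is background. The other planned outputs do not supply the missing rate:

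- **Shift tables (SAP 17.3)** use the normal range at the LOCF endpoints. A patient whose baseline HbA1c is above normal but below 7.5%, and who ends above 7.5%, falls in the same high-to-high cell as one who was above 7.5% throughout. A marked value that has resolved by the endpoint does not show as marked.
- **Mean changes** do not identify individuals.
- **The listing of MAPLV subjects** allows case review but gives no number at risk.

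**Working it through.** The documents state no expected MAPLV rate, so there is no planned figure to reproduce. The check compares the limits, then counts.

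**1. The gap.** 8.4 − 7.5 = 0.9 percentage points of HbA1c. The 8.4% limit governs 80 of 80 + 325 = 405 target patients, or 80/405 = 19.8%. The limit applies to the screening value. Baseline is the last value on or before Day 1, and screening runs up to 14 days, so the two values may differ slightly.

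**2. Would a stable patient in the gap be counted?** Protocol 6.3.2 schedules post-baseline laboratory tests at Visits 4, 6, 8 and 10 (4 tests up to Week 28) and at Visits 12, 14 and 16 (7 tests up to Week 52). Assume a constant true HbA1c, independent normal variation, and a within-patient SD of 0.2 to 0.3. These are assumptions; the documents give none. With p = P(one value ≥ 7.5), the chance of being counted is 1 − (1 − p)^k.

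| True HbA1c | 1 test | 4 tests | 7 tests |
|---|---|---|---|
| 7.5% | 50% | 93.8% | 99.2% |
| 7.7% | 75–84% | 99.6–99.9% | about 100% |
| 8.0% | 95–99% | about 100% | about 100% |

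For example, at 7.5%, p = 0.5 and 1 − 0.5^7 = 0.992. A patient with no change who stays on study is almost certain to be counted.

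**3. Effect per case.**
- New-recruit column: 1/80 = 1.25 points.
- All-patient Week 28 column: 1/405 = 0.247, about 0.25 points.
- Japanese Week 52 total: the documents do not fix the number of Japanese completers. At target numbers the denominator lies between 80 and 405, so the effect lies between 0.25 and 1.25 points.

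**4. Illustration in the 80 new recruits.** Let b be the proportion already marked at baseline and e the new-case rate among the rest (both assumed). If every pre-existing case is counted, the planned percentage is b + (1 − b)e. The baseline-restricted percentage is e, with denominator 80(1 − b).

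| b (patients) | Planned, e = 1% | Planned, e = 2% | At risk |
|---|---|---|---|
| 0 (0) | 1.0% | 2.0% | 80 |
| 1% (0.8) | 2.0% | 3.0% | about 79 |
| 2.5% (2) | 3.5% | 4.5% | 78 |
| 5% (4) | 6.0% | 6.9% | 76 |

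For example, 0.05 + 0.95 × 0.01 = 0.0595. The first row shows that the two counts agree when nobody starts in the marked range.

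**The case against.** **The rule is declared, and it errs towards inclusion.** The SAP says openly that baseline is ignored and labels the values post-baseline, not treatment-emergent or drug-related. The count cannot hide a marked value, and Protocol 9.5.1 states no hypothesis. This stands, and it makes the point one of presentation. It still leaves the reader without a rate of new cases under a heading that promises one.

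**The listed metabolic and prolactin safety variables are not this count.** Protocol 3.4.2 defines them as changes from the DB and LT baselines, which the MAPLV rule does not touch. This stands. A reader might infer that the trial's metabolic and prolactin results as a whole are overstated; the documents do not support that.

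**New onset is partly captured elsewhere.** Clinically significant laboratory findings are recorded as adverse events (Protocol 6.3.1.2), and metabolic TEAEs have their own table (SAP 17.1.5.2). This narrows the gap but does not close it, because that route depends on investigator judgement rather than the Table C limits.

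**Laboratory tests are not alone.** The ECG limits in SAP Table D and the absolute QTc categories also ignore baseline. This is correct, although QTc has separate change-from-baseline categories. The contrast with Table E is therefore supporting evidence, not proof of a broken convention.

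**A baseline-restricted count has its own bias.** For patients given lurasidone in the prior study, LT baseline is Week 6 on drug. Restricting on LT baseline alone would remove abnormalities that arose on drug and persisted. This stands and shapes the fix.

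**Restriction does not isolate a drug effect.** Without a control group, new cases may still reflect disease course or concomitant lithium or valproate. This is true; the split removes only the cases that were present beforehand.

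**Conclusion.** The point holds as a cheap improvement to a supplementary safety table. What rests on the documents alone is that baseline is ignored, that the HbA1c limit of 7.5% lies below the new-recruit entry limit of 8.4%, that the protocol calls the output an incidence, and that no planned table gives a baseline-restricted rate.

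The size is not known. The firm statement is per case: 1.25 points in the new-recruit column and about 0.25 points overall, at target enrolment. The percentages in the illustration depend on assumed values of b and e.

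Two stronger inferences should be avoided. The first is to apply the 7.5-to-8.4% gap to all 405 patients. The 8.4% limit covers only the 80 new recruits, and the prior study's entry limit is not in these documents, so the number of completers starting in the range cannot be judged. The second is to quote a fold-inflation of the reported rate: any such figure would be only a ratio of assumed rates. The count overstates new incidence if any patient starts in the marked range and is counted, and not otherwise.

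**What to change.** Keep the planned MAPLV count. Beside it, for each Table C parameter and treatment group, show the number and percentage with a marked post-baseline value, split by baseline status (marked or not marked, using the same limit), with the number in each stratum as denominator.

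- Use LT baseline for all groups.
- For patients from the prior study, repeat with DB baseline. Read LUR-LUR mainly against DB baseline, because their LT baseline is already on drug.
- New recruits have no DB baseline, so only the LT version applies to them.
- Give patients without a usable baseline value, including a fasting value for the fasting parameters, their own row so that the strata add up to the planned count.

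Neither the entry limit nor the Table C limit needs to change. The data are already collected. The cost is one extra set of columns and smaller denominators, with few patients in the marked-at-baseline stratum.
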